Participants: 110 patients (55 per group) with PD-MCI will be recruited for this study as well as 110 identified and consistent caregivers of the participants. All caregivers will be asked to complete several questionnaires regarding the participant's quality of life and daily functioning prior to the intervention, at follow-up visits, and after the intervention. Although attrition did not occur in Phase I, over-recruitment by 20% will be instituted to account for possible subject attrition or unusable data. Participants will receive a payment of \$40 for each of the four assessments they complete (pre- and post-intervention/support and 6- and 12-month follow-ups).

Procedures: We will primarily recruit Veterans with PD from the VASDHS Neurology and Neuropsychology Clinics. While we will attempt to exhaust recruitment at VA clinics first, recruitment of women may be limited at the VA, and therefore, we will likely need to recruit from outside clinics to obtain a PD-epidemiologically accurate gender ratio of 60 (men)/40 (women). In this regard, we will primarily recruit from the University of California, San Diego (UCSD) Movement Disorders Center. Referred participants will be screened for inclusion/exclusion criteria (please see above) and consented if appropriate. All participants will have Level II MDS-criteria based diagnosis of MCI derived from a formal neuropsychological evaluation within the past 12 months. As most participants will be referred from the VASDHS and UCSD Movement Disorder Center, the majority will have MDS-criteria MCI diagnoses prior to referral. However, should a PD patient be referred for this study who has not had formal neuropsychological testing or if testing is outdated (>12 months), pre-inclusion neuropsychological testing will be performed through [name] lab, which follows patients neuropsychologically. Likewise, if the WRAT-4 Reading scale has not been administered within the past year, this 2-5 minute measure will also be administered to ensure adequate reading level. To avoid confounds, no test proposed as outcome measures in this study will be used to determine the PD-MCI diagnosis.

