Upon meeting study criteria, participants will be randomized to one of two 10-week conditions (CogSMART-PD or Supportive Care). Randomization will occur in blocks (i.e., first 5 people enrolled will be assigned to the intervention group, next 5 will be assigned to control group, next 5 will be assigned to the intervention group, and so on until the sample size of 55 per group is met). Within one to 1.5 weeks prior to beginning the group, participants will be tested by a research assistant blinded to group assignment on a 2-2.5 hour

battery of cognitive, neuropsychiatric, health status/QoL, and strategy use measures as well as a motor assessment (UPDRS-Part III), which will immediately precede the cognitive assessment (please see Assessment/Materials). Participants will be tested in the “on-state” of parkinsonian medications to limit confounding variability (e.g., of motor symptoms, such as tremor) on test results. All participants will be tested at the same time, preferably in the morning, if possible. Breaks will be given during the assessment as needed. Groups will consist of 5 individuals with PD-MCI and be led by a trained clinician (who is not involved in the clinical care or assessment of these participants). Following the intervention and 6- and 12-months post-intervention, PD-MCI participants will be re-tested by a group-blinded research assistant. 24 months post-intervention, participants will be asked to complete a brief (15 minute) telephone interview regarding changes in health status or living situation since the 12-month follow up. Following the 12-month follow-up, the control (support) group will be permitted to join CogSMART-PD.

Assessment/Materials: Outcome measures were carefully selected so that they: 1) represent areas that are frequently impaired, dysfunctional, or problematic for individuals with PD-MCI; 2) correspond to domains that are targeted for improvement by the CogSMART-PD intervention; 3) have adequate psychometric properties for use in PD; and 4) have shown utility and applicability based on the pilot and preliminary studies. Total neuropsychological and motor testing time is estimated to be 2-2.5 hours.

Cognitive Function and Cognitive Strategy Assessment:

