4. Informant Questionnaire on Cognitive Decline in the Elderly (IQCODE)³⁹. The IQCODE is a 26-item, 5-minute informant-based questionnaire used to assess the patient’s everyday functional-based measure of cognition (e.g., recognizing familiar faces, remember things in general, handling financial matters) on a 5-point scale (1=much improved to 5=much worse). The IQCODE has been used fairly extensively in individuals with cognitive impairment and has been found to have high reliability and good validity⁵². In addition, we will also administer the self-report version the IQCODE (IQCODE-SR) to the patients. A psychometric study of the IQCODE-SR found it to have good feasibility, homogeneity, and construct validity⁶⁷. The IQCODE has been used as an outcome in several seminal PD studies (e.g., Aarsland et al., 2009⁶⁸). We conducted a validation study (manuscript in preparation), of the IQCODE in 100 PD patients and found it to have adequate convergent validity with a clinician-measure of cognition (UPDRS Item 1; $r = .39$, $p < .001$) and excellent discriminant validity from measures of motor symptoms (UPDRS-Part III Total; $r = .08$, $p = .41$) and disease severity (Hoehn and Yahr; $r = .11$, $p = .26$).
5. The Montreal Cognitive Assessment (MoCA) will be administered at the baseline (pre-intervention) assessment as a measure of general cognition and will be used as a covariate in the statistical analyses (please see Data Analysis section below). The MoCA is a suitably accurate, brief (10-minute) test of cognitive impairment in PD and has established cut-offs for both PD-MCI and PDD.⁶⁹
6. Cognitive Problems and Strategies Assessment (CPSA)³⁸. The Strategies Assessment section of the CPSA will be used as an assessment of compensatory strategies used by the individual. This questionnaire was found to be sensitive to the use of cognitive strategies after cognitive rehabilitation (CogSMART) participation³⁸. The CPSA takes 8-10 minutes to complete.
7. Parkinson’s disease Cognitive Rating Scale (PD-CRS; Pagonabarraga et al., 2008). This is a cognitive scale specifically designed for individuals with Parkinson’s disease. The assessment has a total of 9 tasks meant to assess attention, working memory, alternating and action verbal fluency, clock drawing, and verbal memory and takes approximately 15 minutes to administer.

Quality of Life, Health Status, and Neuropsychiatric Symptom Assessment:

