Data Analysis: Preliminary analyses will begin with an examination of the distribution of variables to assess their characteristics (means, standard deviations, skewness), to provide descriptive statistics of the study population, and to allow assessment of randomization. Continuous measures will be tested for normality and homogeneity of variance. Non-normally distributed variables will be transformed to meet the normal distribution assumption for linear effects models. Analyses will include tests of randomization and comparability across conditions. Randomization will be tested by performing a series of t-tests and chi-square tests to compare the groups on demographic and initial clinical variables. Pre-specified baseline variables including age, education, gender, severity and duration of illness, and motor symptoms will be considered as potential covariates (as fixed effects) in the multivariate analyses. Any other variables (e.g., baseline cognition as assessed by the MoCA, medications) on which the groups differ initially will also be explored as covariates in subsequent analyses, as described below. In the case of missing data, appropriate data analytic techniques will be used, which may include deletion, imputation, inclusion of an indicator of missing values, or pattern-mixture modeling. Outcomes will be analyzed using SPSS release 16 (SPSS, 2007), and open source statistical software R⁸¹.

As an exploratory aim, we will recruit 60 additional individuals to complete the protocol as described above and in addition, participate in two (pre/post) hour-long brain imaging (fMRI) sessions. The imaging sessions will consist of a structural brain scanning and participation in an fMRI cognitive task (please see below). Following the baseline evaluation, half of the participants will be randomly assigned to the intervention group ($n = 30$) and participate in the CogSMART program. The groups will be broken up to consist of approximately 5 individuals. The remaining participants ($n = 30$) will be assigned to the non-intervention/control ("supportive care") group. This group will also be broken down into groups of 5 when enrolled in the intervention. Participants will be retested by a group assignment-blinded examiner on the clinical and cognitive battery and imaging protocol following the intervention or waitlist.

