27.b1) Is entry of CPRS notes required based on the above criteria?

CPRS notes are needed for ALL subjects
 CPRS notes are needed for SOME subjects
 CPRS notes are NOT needed for any subjects

Identify for which group or groups CPRS records will be entered and to which groups this requirement does not apply.

CPRS notes will be entered for individuals who are consented and attend the treatment sessions. Caregivers who are enrolled into the study do not need CPRS notes because they do not attend treatment sessions nor receive any treatment. Additionally, there are cases where individuals consent to be in the study and complete neuropsychological assessments to determine eligibility but do not end up enrolling into group due to various reasons such as not being able to commit to the 10-week group, loss of interest, etc. In those cases, they do not attend the first day of group and do not receive any treatment; therefore, CPRS notes would not need to be entered for those individuals.

27c) Select the VA Sensitive Information (VASI) use category

This study does not collect or use any VASI
 This study uses but does not save, collect, copy, or record VASI
 This study does collect or record VASI

Section 27.1 VA Sensitive Information (VASI)

27.1a) For each type of VASI, indicate all that apply:

Indicate which of the following will be collected/recorded:

- Protected Health Information (PHI)
- Names
- Device identifiers and serial numbers
- E-mail addresses
- Medical record numbers
- URLs (Universal Resource Locator)
- All elements of dates (except year) or any age over 89
- Health plan beneficiary numbers
- IP Addresses (Internet Protocol)
- Telephone numbers
- Account numbers
- Biometric Identifiers including finger and voice print
- Fax numbers
- Certificate or license numbers
- Full face photographic images and comparable images
- All geographic subdivisions smaller than a state
- Vehicle ID and serial numbers including license plate numbers
- Social security numbers or scrambled SSNs (describe below)
- Other unique identifying number, characteristic, or code (describe below)

27.1a1) Describe why SSN are needed for this study

SSN are needed for subject payment

27.1b) Consent Forms and/or HIPAA Authorization

Yes No

27.1c) Images with personal identifiers are used for this study (x-rays, MRI images with patient names, record numbers, dates, etc.)?

Yes No

27.1d) Photos with faces or audio video recordings are used for this study.

Yes No

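### Phase II assigns the arm before the baseline outcome battery, so no outcome is measured before allocation and self- and informant-rated baselines could shift with the arm

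*Combined protocol and SAP*

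**What the plan says.** The order of events comes from Section 9, Phase II.

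- **Assignment.** Under Procedures: "Upon meeting study criteria, participants will be randomized to one of two 10-week conditions (CogSMART-PD or Supportive Care". The rule follows enrolment order: "first 5 people enrolled will be assigned to the intervention group, next 5 will be assigned to control group", and so on until 55 per group is reached.
- **Baseline battery.** The same paragraph continues: "Within one to 1.5 weeks prior to beginning the group, participants will be tested by a research assistant blinded to group assignment". The battery covers cognition, strategy use, neuropsychiatric symptoms and health status/quality of life.
- **Eligibility testing.** This is separate from the battery: "no test proposed as outcome measures in this study will be used to determine the PD-MCI diagnosis".
- **Use of baseline data.** Under Data Analysis: "Randomization will be tested by performing a series of t-tests and chi-square tests to compare the groups on demographic and initial clinical variables". Under Assessment/Materials, the MoCA "will be administered at the baseline (pre-intervention) assessment as a measure of general cognition and will be used as a covariate".
- **Loss before the first session.** Section 27.b1, on chart notes, mentions people who consent and "complete neuropsychological assessments to determine eligibility but do not end up enrolling into group due to various reasons".
- **The opposite order.** The Data Analysis text also describes 60 additional people in the Phase II imaging cohort. They are to follow the protocol already described, yet their assignment comes after the baseline evaluation.

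**The concern.** A baseline is useful because allocation cannot have influenced it. Here the assignment exists before the baseline is taken. Blinding the tester limits assessor bias, but it does not cover what participants and caregivers report about themselves or each other, or whether they turn up.

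Two things are at stake. First, the ratings behind Aim 2, Aim 3 and the secondary part of Aim 1 could start from a baseline that already reflects reaction to the arm. The affected scales are the IQCODE, IQCODE-SR, CPSA, WHOQOL-BREF and PDQ-39. A baseline difference found by the planned tests could then be an effect of allocation and not chance, and choosing covariates from such differences would adjust for the wrong thing. Second, someone who leaves after assignment but before the battery has been allocated without any baseline on the outcomes. Loss of that kind could differ by arm, since controls may join CogSMART-PD only after the 12-month follow-up.

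**Working it through.** **1. Sequence.** The Procedures text gives: criteria met, then assignment, then the battery 1 to 1.5 weeks before the group, then 10 weekly sessions. That the tester is blinded to group assignment confirms that an assignment exists by then.

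**2. Is there any earlier outcome measurement?** No. Eligibility rests on the Level II neuropsychological evaluation and WRAT-4 Reading, and outcome tests are excluded from the diagnosis.

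**3. Which baselines does tester blinding protect?** Mainly the performance tests: Matrix Reasoning, MIST, Names-Faces, MoCA and PD-CRS. It does not protect the five rating scales named above if the respondent knows the arm. The documents do not say when participants or caregivers learn it.

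**4. Accounting for people assigned.** 2 x 55 = 110, or 55/5 = 11 groups per arm. The text does not say whether the 55 counts people assigned or people who start. No analysis set covers people assigned who never start, and deletion is among the permitted missing-data options.

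**5. Scale, on assumed inputs only.** The Phase II text gives no alpha, power, effect size or SD, so the 110 cannot be reproduced beyond 2 x 55. Assuming two-sided 5% alpha and 80% power, the detectable effect is (1.96 + 0.84) x sqrt(2/55) = 0.53 SD.

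Suppose there is no true effect and knowledge of the arm moves a self-rated baseline by d SD (assumed 0.1 to 0.3) without moving the follow-up score. Let the baseline-outcome correlation be r (assumed 0.5 to 0.8).

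- Change score: bias of size d, SE = sqrt(2(1 - r)) x sqrt(2/55).
- Baseline-adjusted: bias of size r x d, SE = sqrt(1 - r²) x sqrt(2/55).
- The sign of the bias is opposite to that of the shift.

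| r | d | Change-score type I error | Adjusted bias (SD) | Adjusted type I error |
|---|---|---|---|---|
| 0.5 | 0.1 | 8.2% | 0.05 | 6.1% |
| 0.5 | 0.3 | 35.0% | 0.15 | 14.9% |
| 0.8 | 0.1 | 13.2% | 0.08 | 10.8% |
| 0.8 | 0.3 | 70.1% | 0.24 | 55.5% |

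For example, with r = 0.5 and d = 0.1, the change-score SE is 1 x 0.191 = 0.191. The standardised shift is 0.1/0.191 = 0.52 and the rejection rate is 8.2%.

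For loss, suppose the lowest-scoring 5 to 20% leave one arm only, with correlation 0.3 to 0.5 between that score and the outcome (all assumed). With q the fraction lost and c the correlation, bias = c x φ(z_q)/(1 - q). This runs from 0.3 x 0.103/0.95 = 0.03 SD to 0.5 x 0.280/0.80 = 0.18 SD, with type I error of 5% to 14%.

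**The case against.** The best defence is that the primary outcome is a performance test given by a blinded assistant, so the main comparison is fairly well protected. That stands, and it limits the reach of the point. Nor do the Phase II covariates named in the plan include a self- or informant-rated questionnaire, and change scores are specified only for Phase I, although the Phase II hypotheses speak of greater improvement. The plan also reports no attrition in Phase I and provides for 20% over-recruitment.

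A reader might infer four stronger things, none of which the documents support.

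- **That Section 27.b1 shows people leaving after assignment.** It describes people who finished eligibility assessments and then did not join, for reasons that include "do not end up enrolling into group due to various reasons such as not being able to commit to the 10-week group". It names no phase and does not say whether they had been assigned. Under Section 9, anyone lost after meeting Phase II criteria would have been, but that is inference.
- **That people lost before the battery have no data.** They have the eligibility neuropsychological scores and a reading score. These can describe the losses and support imputation or weighting, although they are not baselines on the outcomes.
- **That participants know their arm at baseline.** This is possible and not ruled out, but it is not stated.
- **That moving one sentence cures the problem.** Under the five-then-five rule the arm can be foreseen from enrolment order, whatever the position of the battery.

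**Conclusion.** The point holds for the main Phase II trial: the arm is assigned before any outcome is measured. The exposure falls mainly on the self- and informant-rated secondary outcomes and on the accounting for people assigned who never start. Matrix Reasoning is largely protected.

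The documents do not fix the size. The figures above rest on an assumed shift, correlation and loss fraction; they show what could happen and do not estimate what will. The shift needs respondents to know or guess their arm by the baseline visit. The loss needs people to leave between assignment and the battery, at a rate that the documents do not give.

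The change should be made: it is cheap, a missed baseline cannot be collected later, and the imaging cohort's order shows that the plan already regards assignment after baseline as workable.

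**What to change.** In Section 9, Phase II, Procedures, replace the present order with something like:

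> Consent, eligibility confirmation and the full baseline battery, including informant ratings, are completed before the arm is assigned or revealed to the participant, caregiver or assessor. Assignment then follows a concealed random sequence. Everyone assigned is analysed in the arm assigned, whether or not they attend a session.

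Three edits go with it.

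- Replace the fixed five-then-five rule. One arrangement that suits groups of five is to test ten people and then randomise them 5:5; 110/10 = 11 such cohorts would give 11 groups of five per arm.
- State that the 55 per group counts people assigned, and report losses between assignment and first session by arm, described with the eligibility scores.
- Bring the imaging-cohort text and the main-trial text into one order.

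Tests, visits and staff stay the same. The cost is tighter scheduling between baseline testing, assignment and forming groups: under the arrangement above, ten people instead of five would need testing before a pair of groups starts, which may strain the 1 to 1.5 week window. Setting up a concealed sequence is a small extra task.

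### Phase II allocation is called randomisation but is a fixed alternation of five-person blocks in enrolment order, with no random sequence or concealment described

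*Combined protocol and SAP*

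**What the plan says.** Section 9, Phase II, Procedures states that eligible participants are randomised to CogSMART-PD or supportive care. It then spells out the method, introduced by i.e. and so as a definition, not an example: "first 5 people enrolled will be assigned to the intervention group, next 5 will be assigned to control group", continuing in the same way "and so on until the sample size of 55 per group is met". The block size equals the session-group size of five.

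The Participants paragraph of the same section adds that "over-recruitment by 20% will be instituted to account for possible subject attrition or unusable data". It does not say whether the 110 already includes this.

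Three other provisions bear on the point:

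- **Blinded testing.** At baseline, "Within one to 1.5 weeks prior to beginning the group, participants will be tested by a research assistant blinded to group assignment". Afterwards, "PD-MCI participants will be re-tested by a group-blinded research assistant". Group leaders take no part in assessment.
- **Check on allocation.** In Data Analysis, "Randomization will be tested by performing a series of t-tests and chi-square tests to compare the groups on demographic and initial clinical variables".
- **Covariates.** Also in Data Analysis, "Pre-specified baseline variables including age, education, gender, severity and duration of illness, and motor symptoms will be considered as potential covariates". Under Assessment/Materials, the baseline MoCA "will be used as a covariate in the statistical analyses".

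**The concern.** A random sequence stops anyone from choosing, knowingly or not, who goes into which arm. Concealment stops the next assignment from being foreseen. The stated rule does the first not at all, and no concealment is described.

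Staff influence enrolment order. Under Section 11, research staff telephone candidates, gauge their interest and book the enrolment visit. Section 14 lets a participant who stops early join a later group, and the next block belongs to the other arm. Bringing someone in slightly sooner or later can decide the arm.

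Aim 1 of Phase II is to show that the programme works, and Section 7 supports the study by citing a review that calls for sound randomised trials. Under a known fixed sequence, a difference in Matrix Reasoning at 10 weeks cannot be firmly separated from a difference in who entered each block. Hypothesis 1 concerns improvement, so steering on stable ability would largely cancel if the analysis uses change or adjusts for baseline. What remains is steering on unmeasured factors that predict retest gain or response, such as motivation or expected attendance.

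**Working it through.** **1. The plan's own figure.** Running the rule (five to CogSMART-PD, five to control, repeated) gives 22 blocks, 11 per arm: 11 × 5 = 55 per arm, 110 in total. The stated count is reproduced, and there is exactly one possible sequence.

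**2. Predictability for someone who knows the enrolment count.**

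| Method | Correct predictions |
|---|---|
| Current rule | 110 of 110 (100%) |
| Sets of ten, split at random after baseline | 50% (no arm exists yet at enrolment) |
| Random order within pairs of five-person cohorts | up to (50% + 100%)/2 = 75%; 11 of 22 cohorts deducible |

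**3. Over-recruitment.** If the 20% is additional to 110, the total is 110 × 1.2 = 132 (13 sets of ten plus 2) or 110/0.8 = 137.5, so 138 (13 sets plus 8). Continuing the present alternation past 110 would give 67 v 65 or 70 v 68. The rule covers neither case, since it stops at 55 per group.

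**4. Illustration of bias.** The documents give no basis for a shift, so the shift b is an assumption throughout, in SD units, with no true effect, 55 per arm, a two-sided 5% test and independent outcomes.

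- *Unadjusted comparison:* noncentral t, df = 108, noncentrality b × √(55/2).
- *Baseline-adjusted, steering only on stable ability:* the same shift b is present at baseline and outcome, with assumed correlation r. The effective shift is b × √((1 − r)/(1 + r)), df = 107. For b = 0.3 and r = 0.5 this is 0.3 × √(0.5/1.5) = 0.173.
- *Change scores, same steering:* the shift cancels.

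| Assumed b | Unadjusted | Adjusted, r = 0.5 | Adjusted, r = 0.7 | Change score |
|---|---|---|---|---|
| 0.1 | 8.2% | 6.0% | 5.6% | about 5% |
| 0.2 | 18.0% | 9.2% | 7.2% | about 5% |
| 0.3 | 34.5% | 14.7% | 10.0% | about 5% |

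Simulation (4,000 runs each) gave similar or slightly lower adjusted rates (at b = 0.3: 13.3% for r = 0.5 and 9.2% for r = 0.7), and 4.8% to 5.6% for change scores. The adjusted and change-score columns do not cover steering on factors that predict gain itself. Neither method removes that.

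**5. If enrolment is already under way.** With 20, 40 or 60 of 110 people allocated by the old rule, (110 − 20)/2 = 45, 35 or 25 per arm remain to be randomised. The difference detectable with 80% power (unadjusted two-sided 5% t-test, clustering ignored) is 0.54 SD with 55 per arm, and 0.60, 0.68 or 0.81 SD with 45, 35 or 25.

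**The case against.** The strongest reply is that predictability needs someone who tracks the count. Referrals come from several clinics, a diagnosis-code search, letters to former study participants and community sources, and nothing shows that referring clinicians know the running total. The absence of concealment is inferred from silence, and part of the staff-role text in Section 21 was not available to us. Testers are blinded, covariates are planned and the hypothesis concerns improvement, so the unadjusted rates overstate the risk under a change or baseline-adjusted analysis. A net shift of 0.3 SD is also large: one route is 30% of participants steered with a 1 SD prognostic difference (0.30 × 1 = 0.30).

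Much of this stands as a limit on size. The documents do not show that selection occurs, and the illustrative rates are not estimates.

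It does not rescue the method. The rule is printed, so a fixed sequence is predictable to any recruiter who knows the count, whoever else does not. Blinded testing addresses detection bias, not selection. The t-tests and chi-square tests compare measured variables only and cannot test a random process that is absent. The covariates also cover only what is measured. The Data Analysis text does not say whether the primary comparison uses change or baseline adjustment, so even the partial protection against steering on ability is not assured.

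A narrower point also remains: a blinded tester who learned a participant's enrolment position could work out the arm.

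**Conclusion.** The concern holds, with high confidence. As written, the main Phase II comparison uses systematic alternation by blocks of five, and calling it randomised would be inaccurate whether or not anyone steers enrolment. All 110 assignments are determined in advance.

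The possible bias has no estimate in the documents. Under assumed shifts of 0.1 to 0.3 SD, false rejection ranges from about 5% (change scores, steering on stable ability only) to about 34% (unadjusted). The allocation rule should be corrected before the trial is presented as randomised. The conclusion on predictability rests only on the printed rule. The conclusion on concealment rests on none being described in the text available.

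**What to change.** **Main change.** Replace the rule in Section 9, Phase II, Procedures with a computer-generated sequence held by an existing team member who neither recruits nor tests. Enrol ten people, complete their baselines, then split them at random into one CogSMART-PD group and one supportive-care group of five. In the same amendment:

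- Reconcile this with the baseline window of 1 to 1.5 weeks, by scheduling the ten baselines together or by amending the window.
- State whether 110 includes the 20% over-recruitment. If it is additional, recruit whole sets (130 or 140 people), or state that a final incomplete set is split at random into equal halves, with the arm of any odd person also drawn at random.
- State that testers have no access to the enrolment log.

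**Lesser alternative, if two groups cannot run at once.** Randomise the order of arms within each pair of five-person cohorts, and reveal the arm only after the whole cohort is enrolled and baseline-tested. This is weaker: the second arm of a pair can be deduced once the first is known, and the cohort becomes the randomised unit, which the analysis must reflect.

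**If enrolment has begun.** The documents do not settle this. Section 27 (27.b1) refers in the present tense to people who consent and are tested but do not join a group, without naming the phase. Apply the new rule to the remaining participants and report earlier blocks as non-randomised. Before any outcome is compared by arm, state who forms the primary analysis: for example, everyone, with allocation rule as a stratum, plus a sensitivity analysis limited to those randomised.

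**If enrolment is complete.** Describe the allocation as systematic alternation.

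**Cost.** Before enrolment, a one-paragraph amendment and a list, with no extra visits. At 110 people there are 11 whole sets and no extra patients. With additional over-recruitment, whole sets mean two fewer people (130 v 132) or two more (140 v 138).

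The real costs are practical. Waits are longer, with some possible loss, while ten rather than five people accumulate. Baseline testing takes 10 × 2 to 2.5 = 20 to 25 hours per window instead of 10 to 12.5, each session including a neurologist's motor examination. Two groups running together need 2 × 1.5 = 3 facilitator hours a week instead of 1.5, and the documents do not show whether that can be staffed. If enrolment has begun, an analysis limited to the randomised participants also loses power, as shown above.
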